8.2 Statistical Analysis Plan

8.2.1 Analysis of Overall Conduct of Study

Enrollment and major protocol violations, study treatment administration, and reasons for subject discontinuations from the study treatment will be described and listed or summarized.

Demographic and baseline characteristics, such as age, sex, histology, prior nephrectomy status, site(s) of metastatic disease, prior treatments including response and duration, MSKCC renal cell carcinoma risk stratification, and baseline ECOG performance status will be summarized.

8.2.2 Analysis of Safety

Safety will be assessed through summaries of DLTs, adverse events, clinically significant changes in laboratory test results, clinically significant changes in vital signs and ECGs, and exposure to components of study treatment. All subjects who receive any amount of study treatment will be included in the safety analyses.

Adverse event data will be listed by dose cohort. Events occurring on or after treatment on Cycle 1, Day 1 will be summarized by AE term, NCI CTCAE v4.0 grade, and relationship to either pembrolizumab and/or cabozantinib.

Serious adverse events, including deaths, will be listed separately and summarized.

Adverse events leading to treatment discontinuation will be listed.

Adverse events meeting the criteria for DLT will be listed. Subjects who withdraw from the study prior to completing the DLT assessment window for reasons other than a DLT will be considered unevaluable for DLT assessments.

8.2.3 Analysis of Anti-Tumor Activity

Descriptive statistics will be used to summarize all demographic and analytic data. Continuous data will be summarized using means, standard deviation, range, etc. Categorical data will be summarized using frequency tables.

Tumor response analyses will be based on definitions of responses according to both RECIST v1.1 and immune-related response criteria (irRECIST).

Objective response is defined as a complete or partial response, as determined by investigator assessment using RECIST and irRECIST. Subjects with missing or no response assessments will be classified as non-responders. For the primary objective, a one-sided exact binomial test will be used to assess whether the ORR is significantly greater than 20% in subjects taking a combination of pembrolizumab and cabozantinib.

Clinical benefit rate (CR + PR +SD) and duration will also be recorded.

Among subjects with an objective response, duration of response will be defined as the time from first occurrence of a documented objective response until the time of documented disease progression or death from any cause during the study, whichever occurs first. For all other subjects, duration of objective response will be censored at the day of the last tumor assessment.

Progression-free survival (PFS) will be defined as the time from study treatment initiation (Cycle 1, Day 1) to the first occurrence of documented disease progression or death from any cause during the study, whichever occurs first. For subjects who do not have documented progressive disease or death during the study, PFS will be censored at the day of the last tumor assessment.

Overall survival (OS) will be defined as the time from study treatment initiation (Cycle 1, Day 1) to death from any cause. For subjects who do not have documented death during or after the study, OS will be censored at the day of known survival status.

In subjects with bone metastases, time to progression of bone metastases or skeletal related event (SRE, defined as pathologic fracture, spinal cord compression, and radiation to bone or surgery to bone related to cancer) will also be recorded from Cycle 1 Day 1 to the time of progression or SRE.

Progression-free survival, overall survival, duration of response/duration on treatment, and time to skeletal related event or bone progression will be assessed using Kaplan-Meier curves and hazard ratios. The clinical benefit rate and duration of clinical benefit will be summarized using descriptive statistics.

Among subjects who receive treatment beyond progression, duration on treatment will be recorded.

Response data may be listed, summarized in tables, and/or presented as a swimmer plot.

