5.2.1.3.2 Pembrolizumab Second Course

The participant's initial course of treatment with pembrolizumab will be the First Course, and in the absence of disease progression may be administered for up to 35 cycles. After the First Course, all participants who stop pembrolizumab after 35 cycles with SD or better may be eligible for up to an additional 17 cycles (approximately 1 year) of pembrolizumab treatment if they progress after stopping pembrolizumab from the initial treatment phase.

This retreatment is termed the Second Course phase and is only available if the participant continues on cabozantinib monotherapy and remains on study after completing the First Course of pembrolizumab and meets the following conditions:

Either

- Stopped initial study intervention after attaining an investigator-determined confirmed CR based on RECIST 1.1, and
 - Was treated with at least 8 cycles of pembrolizumab before discontinuing treatment, and
 - Received at least 2 treatments with pembrolizumab beyond the date when the initial CR was declared

OR

• Had SD, PR, or CR and stopped pembrolizumab after completion of 35 administrations (approximately 2 years) of study intervention for reasons other than disease progression or intolerability

AND

- Experienced an investigator-determined radiographic disease progression by RECIST 1.1 after stopping initial treatment, and
 - The participant meets all of the safety parameters listed in the inclusion criteria and none of the safety parameters listed in the exclusion criteria, and
 - The patient remained on study while still continuing to dose with cabozantinib monotherapy after stopping initial pembrolizumab treatment (First Course).

Additionally, the treating physician must determine at the time of progression after stopping initial treatment that continuing cabozantinib and resuming pembrolizumab is the best treatment course for the patient.

An objective response or disease progression that occurs during the Second Course Phase for a participant will not be counted as an event for the primary analysis of either endpoint in this study.

Participants who have experienced an initial disease progression by RECIST 1.1 and have an iSD, iPR,or iCR per iRECIST after completion of 35 administrations of study intervention for reasons other than disease progression or intolerability may be considered for the Second Course Phase after consultation with the Sponsor-Investigator.

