5.2.3 Trial Blinding/Masking and Treatment Allocation

This is an open-label trial; therefore, the investigator and subject will know the treatment administered. This is a single arm, open-label study. All subjects will receive the combination of pembrolizumab and cabozantinib.

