| Scheduling Window (Days): | -28 to -1 | | ± 3 | ± 3 | ± 3 | ± 3 | ± 3 | ± 3 | Within 30 days post treatment discontinuation | ±1 month |
| Tumor Imaging ^e (CT or MRI C/A/P +/- Whole Body Bone Scan ^d) | х | | | | X | | | х | | |
| RECIST 1.1 and irRECIST radiology read ^c | Х | | | | Х | | | Х | | |
| Archival Tumor Collection | Х | | | | | | | | | |
| Optional Fresh Tumor Biopsies (baseline and post-treatment) | Xe | | Xe | | | | | | | |
| • PD-L1 Testing | Х | | Х | | | | | | | |
| Immuno-Oncology Marker Testing | X | | X | | | | | | | |
| Correlative Studies | | | | | | | | | | |
| Bone Turnover Markers^g (in subjects with bone metastases only) | | Х | Х | | Х | | | X† | | |

^a Each treatment cycle = 3 weeks.

^b Urine pregnancy test is required only in women of childbearing potential.

^c CT or MRI CAP +/- bone scan and RECIST 1.1 assessments will be obtained at baseline and after every 3 cycles. irRECIST = immune-related response criteria. PET/CT is an acceptable alternative imaging modality. All scans can be performed \pm 7 days from the scheduled date.

d Whole Body Bone Scan is required for subjects with known or suspected bone metastases. All scans can be performed \pm 7 days from the scheduled date.

^e The baseline optional fresh tumor biopsy should be obtained during the screening period, prior to C1D1 treatment. The post-treatment optional fresh tumor biopsy should be obtained approximately 3-6 weeks (during cycle 2). Subjects may consent for separately for either baseline and/or post-treatment biopsies.

g Bone turnover markers may include β C-terminal telopeptide (β-CTX), bone specific alkaline phosphatase, and procollagen type 1 amino-terminal propeptide (P1NP). †Bone turnover markers will be collected through cycle 7 but not beyond. Bone tumor markers are not required during the second course of treatment.

ⁱ Total T3 = Total thriiodothyronine, Free T4= T4 (thyroxine) Free

^j Screening labs and pregnancy tests do not need to be repeated at C1D1 if done within 7 days of C1D1.

^k EKG tests will be performed through cycle 7, and then only as clinically indicated.

¹ In the absence of disease progression, pembrolizumab may be administered for up to 35 cycles (first course). If the patient progresses after discontinuing pembrolizumab, they may resume dosing for up to 17 additional cycles (second course), providing they meet criteria for retreatment. See protocol section 5.2.1 for additional information.

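### Section 8.2.3 does not require a CR or PR to be confirmed before it counts toward the primary ORR, so a single-scan response can count in a single-arm test against a fixed 20%

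*Combined protocol and SAP*

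**What the plan says.** **Endpoint.** Section 8.2.3: "Objective response is defined as a complete or partial response, as determined by investigator assessment using RECIST and irRECIST". For the primary objective, "a one-sided exact binomial test will be used to assess whether the ORR is significantly greater than 20"%. Duration of response is the "time from first occurrence of a documented objective response" to progression or death. "Subjects with missing or no response assessments will be classified as non-responders".

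**Setting.** Section 5.2.3: "This is an open-label trial; therefore, the investigator and subject will know the treatment administered". There is one arm.

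**Confirmation elsewhere.** One route into the pembrolizumab Second Course (5.2.1.3.2) needs an "investigator-determined confirmed CR based on RECIST 1.1". Sections 5.6.2 and 5.7 refer to confirmed radiographic progression. The irRECIST table in 12.4.2 asks for a later assessment to confirm irPD and says irSD needs no confirmation. Its irCR and irPR rows do not mention confirmation. Section 12.3 adopts RECIST 1.1 by citing the publication and reproduces no confirmation rule.

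**Scans.** Sections 6.0 and 7.1.2.5 set imaging at baseline and after every 3 cycles of 3 weeks, with a 7-day window either way. The chart in 6.0 also lists a "RECIST 1.1 and irRECIST radiology read" at the imaging visits.

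**Decision rule.** Section 8.2.5 stops at 2 or fewer responses in 20 and declares success above 12 in 38. It gives type I error 0.029 (limit 0.05), power 98% (constraint 90%), probability of early termination 0.206 and expected sample size 34.29. Section 2.1.7 instead stops below 2 in 20 and declares success at 12 or more in 38.

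**The concern.** The observed response rate is compared with a constant, so no control arm carries the same reading error and cancels it. If the 20% stands for responses that last to a second scan, while the trial counts any CR or PR seen once, the numerator is more generous than the benchmark. The investigator making the call knows the treatment. The protocol names confirmation for one retreatment route and for progression, but not for the endpoint that decides the trial. What is at stake is whether the stated type I error of 0.029 describes the test that will be run.

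**Working it through.** **Inputs.** From 8.2.5: n1 = 20, stop if 2 or fewer; N = 38, success if 13 or more; null 0.20, alternative 0.50. From 6.0 and 7.1.2.5: 3 cycles × 3 weeks = 9 weeks between scans. The documents give no rate of single-scan calls that later fail, so that rate is an assumption and is varied below.

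**Formulas.** Write b(x; n, p) for the binomial probability.
- Early termination: PET(p) = Σ b(x; 20, p) over x = 0 to 2.
- Declaring efficacy: S(p) = Σ b(x; 20, p) × P(X2 ≥ 13 − x), over x = 3 to 20, with X2 binomial(18, p).

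**Step 1: reproduce the plan's figures.**
- PET(0.20) = 0.0115 + 0.0576 + 0.1369 = 0.206.
- Expected N = 20 + 18 × (1 − 0.20608) = 34.29.
- S(0.20) = 0.0288 and S(0.50) = 0.9832.

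All agree with 8.2.5. The 2.1.7 rule gives type I error 0.0623, PET 0.069 and expected N 36.75, so the stated 0.029 belongs to the 8.2.5 rule.

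**Step 2: add single-scan calls under the null.** Assume the true confirmed ORR is 0.20 and that calls which would not be confirmed add d, so the observed rate is 0.20 + d and the expected number of extra responders is 38d.

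| d | Observed rate | Extra responders in 38 | S, 8.2.5 rule |
|---|---|---|---|
| 0 | 0.20 | 0 | 0.029 |
| 0.02 | 0.22 | 0.76 | 0.058 |
| 0.04 | 0.24 | 1.52 | 0.102 |
| 0.05 | 0.25 | 1.90 | 0.132 |

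Solving S(p) = 0.05 gives p = 0.2157, that is 38 × 0.0157 = 0.6 extra responders on average.

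**Step 3: what it takes to reach the bar.** An inactive regimen averages 38 × 0.20 = 7.6 responses. The gap to 13 is 5.4, so an average inactive trial would need 5 to 6 such calls. At d = 0.05 it still fails with probability 1 − 0.132 = 0.868.

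**Step 4: effect of requiring confirmation.** Under the same assumption the null rate returns to 0.20 and type I error to 0.029. If a share L of true responders is not confirmed, the rate at the alternative is 0.50 × (1 − L).

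| L | Rate | Power |
|---|---|---|
| 0 | 0.500 | 0.983 |
| 5% | 0.475 | 0.965 |
| 10% | 0.450 | 0.935 |
| 15% | 0.425 | 0.885 |

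The 90% constraint holds at a 10% loss but not at 15%.

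**The case against.** **The plan may already imply confirmation.** A reader might infer that the protocol deliberately counts unconfirmed responses. The documents do not go that far. They are silent, and RECIST 1.1 enters by citation, so a confirmation rule could be read in from the source; the Second Course wording is compatible with that. What stands is that 8.2.3 leaves the matter open and, as written, lets a single-scan response count.

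**An existing independent read is being ignored.** This too is tempting, because 6.0 schedules a radiology read. But nothing describes it as independent, central or blinded, and nothing shows that the investigator's assessment is separate from it. Moving the endpoint to that read would not necessarily remove any bias, and a truly independent reader would be an added resource. This part should not be pressed.

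**A few soft PRs would carry an inactive regimen to success.** Step 3 shows otherwise: the probability of a false success rises, but failure remains the usual outcome. Nor does every error favour success. Responders can be missed, and missing assessments count as non-response.

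**The inflation is assumed.** This is correct. If 20% was itself drawn from unconfirmed investigator-read rates, the inflation shrinks or disappears.

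**Confirmation has a cost.** It does. The chart in 6.0 shows no imaging at the end-of-treatment visit. Section 5.6.3 promises disease follow-up for subjects who stop without progression but gives no scan schedule for it. A responder who stops after one scan may therefore never have a second.

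**It is late to change the endpoint.** Section 5.2.1.3.2 allows for subjects already past 35 cycles at the October 2020 version. In an open-label trial, responses may be known when the rule is written. This argues for dating the change and reporting both counts, not for leaving the rule unstated.

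**Conclusion.** The point holds as a gap in the primary endpoint definition. Under the 8.2.5 rule the false-positive probability goes from 0.029 to between 0.058 and 0.132 when single-scan calls add 2 to 5 points. It passes 0.05 once the observed null rate reaches about 21.6%. These figures rest on two assumptions that the documents neither support nor exclude: that the 20% null is a confirmed rate, and that single-scan calls add points of that order. The trial is not invalidated, but its type I margin is thin enough for the rule to be written down.

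The unresolved bar makes this worse. If 2.1.7 governed, type I error would be 0.062 before any single-scan call is added, and 0.112 or 0.181 at observed rates of 22% or 24%.

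**What to change.** In 8.2.3:

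1. Define the primary response as a CR or PR that is confirmed at the next scheduled 9-week assessment.
2. Report unconfirmed ORR as a sensitivity analysis.
3. Count responders with no second scan as non-responders in the primary analysis, list them, and count them as responders in the sensitivity analysis.
4. Keep the first of the two scan dates as the start of duration of response.
5. State the date of the change and whether response counts were known by then.

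Separately, reconcile the success bars in 2.1.7 (at least 12) and 8.2.5 (more than 12), and the futility rules beside them. The printed operating characteristics match 8.2.5 only.

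**Cost.** No scans are added for subjects who stay on the imaging schedule. The reported ORR will be slightly lower. The Stage 1 and final counts wait up to one scan interval. Power falls as in step 4, so the sponsor should state the loss it expects; at 15% the design misses its own 90% constraint.

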2.1.7 Phase II Dose Expansion

A Simon two-stage design will be used. Based on the primary endpoint of objective response rate, twenty evaluable subjects will be enrolled in Stage I portion of Phase II. If there are at least 2 responses among the 20 evaluable subjects, an additional 18 evaluable subjects will be entered. If there are fewer than 2 responses among the first twenty evaluable subjects, then this trial will be stopped early for futility. If at least 12 are observed among the 38 evaluable subjects, then the treatment will be considered effective.

Subjects from the Phase I part of the study who are treated at the RP2D may be included in the efficacy assessments in Stage I of the Phase II part of the study.

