8.0 STATISTICAL ANALYSIS PLAN

8.1 Statistical Analysis Plan Summary

The final study analysis will be based on subject data collected through study discontinuation. Analyses will be based on the safety-evaluable population, defined as all subjects who receive any amount of study treatment. In general, data will be summarized as warranted, and listings will be provided in place of tables when sample sizes are small. Summaries will be presented by the assigned dose regimen and designated treatment arm.

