8.2.5 Sample Size

The proposed study is a single-arm, phase I/II study of pembrolizumab in combination with cabozantinib in subjects with metastatic RCC. We will use a Simon two-stage design for the phase II portion this study based on the primary endpoint of objective response rate. The planned enrollment for this study is approximately 25-55 total subjects, to account for screen failures, in order to achieve 6-9 evaluable subjects in Phase I dose escalation and 20-38 evaluable subjects in Phase II dose expansion. Subjects from the Phase I part of the study who are treated at the RP2D may be included in the efficacy assessments in Stage I of the Phase II part of the study.

Phase I:

Any subject who does not complete the DLT assessment window for any reason other than a DLT will be considered non-evaluable for dose-escalation decisions and MTD and RP2D assessment and will be replaced by an additional subject at that same dose level.

Table 12 describes the probability of not observing any DLTs in 3 subjects, and the probability of observing fewer than two DLTs in 6 subjects for different underlying DLT rates.

| Underlying DLT Rate | Probability of Observing No DLTs in 3 Subjects | Probability of Observing Fewer Than Two DLTs in 6 Subjects |
|---------------------|---|---|
| 0.10 | 0.73 | 0.89 |
| 0.20 | 0.51 | 0.66 |
| 0.33 | 0.30 | 0.36 |
| 0.40 | 0.22 | 0.23 |
| 0.50 | 0.13 | 0.11 |
| 0.60 | 0.06 | 0.04 |

Table 12: Probability of Observing DLTs for Different Underlying DLT Rates

For a given adverse event with a true rate of 10%, 5%, or 1%, the probability of observing at least one such adverse event in a given cohort of 6 subjects is 47%, 26.5%, and 5.8%, respectively.

Phase II:

The Simon's two-stage design will be implemented to test the null hypothesis that $ORR \le 0.20$ versus the alternative that $ORR \ge 0.50$. After the enrollment of 20 evaluable patients in the first stage, the trial will be terminated if 2 or fewer respond. If the trial goes on to the second stage, a total of 38 patients will be studied. If the total number responding is greater than 12, the treatment is considered effective.

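### The primary exact test in 8.2.3 is not tied to the 38 RP2D subjects on whom 8.2.5 decides success, so the two verdicts can differ

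*Combined protocol and SAP*

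**What the plan says.** - **Primary test (8.2.3).** A one-sided exact binomial test asks "whether the ORR is significantly greater than 20% in subjects taking a combination of pembrolizumab and cabozantinib". No dose level, phase, N or significance level is given. The same section adds: "Subjects with missing or no response assessments will be classified as non-responders".
- **Population (8.1).** "Analyses will be based on the safety-evaluable population, defined as all subjects who receive any amount of study treatment". This is the only general analysis population in the plan. No efficacy population is defined, and neither is evaluability for response.
- **Decision rule (8.2.5).** A Simon two-stage design with null ORR 0.20 and alternative 0.50: 20 evaluable subjects, stop at 2 or fewer responses, otherwise continue to 38. "If the total number responding is greater than 12, the treatment is considered effective".
- **Phase I subjects in the Simon count (2.1.7, repeated in 8.2.5).** "Subjects from the Phase I part of the study who are treated at the RP2D may be included in the efficacy assessments". This applies to Stage I, and nothing there admits subjects treated at another dose.
- **Intent (4.2.1).** The Phase II part is described as evaluating ORR at the RP2D.

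**The concern.** The plan gives two routes to a primary conclusion and does not say that they use the same subjects. Every Phase I subject receives the combination, so the wording of 8.2.3, read with 8.1, takes in subjects at a dose that was not selected. The Simon count leaves them out.

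Such subjects are expected. Under 2.1.3 and 4.2.2.2, 40 mg opens first and the next cohort is 60 mg or 20 mg depending on DLTs, with at least 3 subjects per cohort. A trial that reaches 38 RP2D subjects will therefore probably have treated 41 or more.

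Two things are at stake. A claim about the RP2D could rest partly on responses at another dose. And in an open-label, single-arm trial with investigator-assessed response, the choice between two populations could be made after the responses are known.

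**Working it through.** **Inputs.** Null ORR 0.20, alternative 0.50, n1 = 20 (stop at ≤ 2), N = 38 (success at ≥ 13) and the 0.05 error limit, all from 8.2.5. Minimum of 3 per cohort from 2.1.3. Assumptions: the test is run at one-sided 0.05 and covers all treated subjects.

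**1. Reproduce the plan's figures.**
- Probability of early termination = P(X ≤ 2 | 20, 0.20) = 0.206.
- Expected N = 20 + 18 × (1 − 0.206) = 34.29.
- P(success) = Σ over x₁ ≥ 3 of P(x₁ | 20, p) × P(X₂ ≥ 13 − x₁ | 18, p). This is 0.029 at p = 0.20 and 0.983 at p = 0.50.

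All agree with 8.2.5.

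**2. Exact test on the same 38 subjects.** p-value = P(X ≥ r | N, 0.20) = Σ from x = r to N of C(N, x) 0.2^x 0.8^(N−x). At N = 38, r = 12 gives 0.062 and r = 13 gives 0.029. The critical count is 13, which is the 8.2.5 rule.

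**3. Exact test with m further treated subjects (N = 38 + m).** The critical count is 13 for N = 38–40 and 14 for N = 41–44.

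| In the 38 | Outside | Total | p | 8.2.5 | Test |
|---|---|---|---|---|---|
| 12 | 1/1 | 13/39 | 0.036 | failure | success |
| 13 | 0/3 | 13/41 | 0.052 | success | failure |
| 12 | 2/3 | 14/41 | 0.024 | failure | success |
| 13 | 0/6 | 13/44 | 0.086 | success | failure |

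**4. Chance of opposite verdicts.** Let x = x₁ + x₂ be responses in the 38, y responses in the m others, c the critical count at 38 + m, and q the ORR at the other dose. Sum P(x₁ | 20, p) P(x₂ | 18, p) P(y | m, q) over x₁ ≥ 3 and all outcomes where exactly one of x ≥ 13 and x + y ≥ c holds. A trial stopped at Stage I has at most 2 + m responses in 20 + m subjects. For m = 3 or 6 that is never significant, so it adds no conflict.

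| m | True RP2D ORR p | q = p | q = p/2 | q = 0 |
|---|---|---|---|---|
| 3 | 0.20 | 1.3% | 1.3% | 1.7% |
| 3 | 0.35 | 7.6% | 8.6% | 13.5% |
| 3 | 0.50 | 0.8% | 1.0% | 2.0% |
| 6 | 0.35 | 14.1% | 8.6% | 13.5% |

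Hand check for q = 0: conflict then requires exactly 13 responses in the 38. At p = 0.20 that is P(X ≥ 13) − P(X ≥ 14) = 0.0288 − 0.0120 = 0.0168, or 1.7%.

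**5. Which m is plausible.** The plan expects 6–9 evaluable Phase I subjects. If six are at the RP2D, as the x/6 rule in 2.1.5 implies, at most 9 − 6 = 3 are elsewhere. So m = 3 is the main case and m = 6 an upper one.

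**The case against.** The strongest reply is that 8.2.3 and 8.2.5 describe one rule twice. The exact test on 38 subjects has critical count 13 and p = 0.029, which are the boundary and the type I error stated in 8.2.5. Section 8.1 speaks of a safety-evaluable population in a general summary, and specific sections depart from it: 8.2.2 excludes early withdrawals from DLT assessment. Letting RP2D subjects from Phase I into the efficacy assessment would have little purpose if all Phase I subjects were already in the primary test. Section 4.2.1 also ties Phase II efficacy to the RP2D.

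Much of this stands. RP2D-only intent is plausible, and 8.2.3 does not itself say that all doses are pooled. But the intent is never applied to the test, and 8.1 is the only general population a programmer would find. Its by-dose sentence concerns summaries and does not restrict the test. Section 8.2.2 separately places all treated subjects in the safety analyses, so 8.1 is not naturally read as covering safety alone.

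Three stronger readings go too far:
- A reader might infer that the plan mandates contradictory verdicts. It does not; the conflict depends on the all-treated reading.
- A reader might infer that the rules agree while N is 38–40, because the critical count stays at 13. An equal count does not mean equal verdicts, as 13/39 shows.
- A reader might infer an inflated type I error. If all doses share an ORR of 0.20, the all-treated test alone has error 2.4% at N = 41 and 4.4% at N = 44, both below 0.05. Extra error arises only if either rule may declare success.

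**Conclusion.** The point holds as a gap in specification that affects the primary conclusion. The plan does not state the population for its primary test, and the only general population it gives differs from the set on which success is decided. On the all-treated reading, the verdicts can differ as soon as one treated subject lies outside the 38.

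With three such subjects, the chance of conflict is small at the design hypotheses (about 1–2%) and appreciable near the boundary (7.6–13.5% at a true ORR of 0.35). With six it is 8.6–14.1% at 0.35. These figures rest on the inferred population, on 0.05 borrowed from 8.2.5, and on the ORR assumed at the other dose.

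Treated RP2D subjects who are not counted as evaluable could widen the gap, because 8.2.3 makes missing assessments non-responses while the Simon count takes evaluable subjects only. The design figures in 8.2.5 are correct and are not in question.

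**What to change.** - In 8.2.3, state that the primary analysis is the 8.2.5 Simon decision in the 38 RP2D subjects (Stages I and II together), and that the exact binomial test is run on that same set at a stated one-sided level.
- In 8.1, limit the safety-evaluable population to safety analyses and descriptive summaries.
- Report responses in Phase I subjects at other dose levels separately, by dose.

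The cost is SAP wording only. The downside is that responses at non-selected doses no longer count in the primary test.

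Aligning the populations does not settle a separate contradiction, which must also be reconciled. Section 2.1.7 continues at 2 responses in Stage I and declares success at 12, whereas 8.2.5 stops at 2 and requires 13. Only the 8.2.5 boundaries reproduce the stated operating characteristics; 12/38 gives p = 0.062 even on the 38 alone.
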